inhibitor, and reduced ASC-speck formation implicated in classical inflammasome formation and activity (Bonnekoh et al. 2021). These processes may differ between patients and animal models utilised and may not yet be fully elucidated, however disulfiram consistently demonstrated significant beneficial effects via GSDMD inhibition. Further, disulfiram treatment was also shown to reduce histone H3 processing in neutrophils after LPS stimulation, a process concomitant with NETosis (Adrover et al. 2022). GSDMD is involved in pore-formation in neutrophil granules intracellularly, which releases NE that then acts in a positive feedback loop to activate GSDMD and promote NETosis (Sollberger et al. 2018), and reduced spontaneous NETosis when neutrophils from septic patients were treated directly with disulfiram in vitro (Silva et al. 2021). In cancer cells including malignant T-cells, disulfiram treatment has been shown to induce apoptosis and inhibit proliferation (Chen et al. 2022), these mechanisms may be cell-type specific and there is so strong evidence that apoptosis is promoted in other non-cancer cell types. On the contrary, in addition to reducing NETosis, disulfiram can act on other immune cell types to reduce harmful methods of cell death including the explosive macrophage pyroptosis. Neutrophils are not the only player in the lungs in bronchiectasis and are influenced significantly by the inflammatory environment they encounter. By impacting the proinflammatory activity of multiple cell types neutrophilic inflammation may also be quiesced.

Based on existing clinical practice, where doses of >200mg are frequently used, as well as from safety data from clinical trials, there have been no major safety concerns identified with the use of 400mg disulfiram daily. While the SmPC states that the maximum Disulfiram dose is 200mg once daily, that is in a context of a treatment duration up to six months, for patients with alcohol dependency. In the British National Formulary and clinical practice the maximum dose goes up to 500mg once daily for the treatment of alcohol dependence over a similar period, under supervision. As the recruitment cohort are not individuals with alcohol dependency, as well as excluding individuals with any major cardiovascular disease/liver/psychiatric diseases, it is thought that there are no major safety concerns about using the dose of Disulfiram 400mg once daily dose for only 28 days.

Arm 3: Dipyridamole

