2.1. Assessment and Management of Risk

This trial is categorised as: Type B = Somewhat higher than the risk of standard medical care

The trial treatments are all repurposed drugs already approved for use in conditions other than bronchiectasis.

Arm 1: Usual care

Arm 2: Disulfiram

Disulfiram is an alcohol deterrent compound licensed for use as an adjuvant in the treatment of drinking problems. The most common adverse reaction (AR) reported during treatment is alcohol reaction. Disulfiram–ethanol reactions often develop within 15 minutes after exposure to ethanol; symptoms usually peak within 30 minutes to 1 hour, and then gradually subside over the next few hours. Symptoms may be severe and life-threatening. Participants will be informed of the reaction risk and must agree to abstain from alcohol during treatment and for up to 14 days after discontinuation.

Arm 3: Dipyridamole

Dipyridamole is licensed for use in secondary prevention of ischaemic stroke and transient ischaemic attacks and as an adjunct to oral anti-coagulation for prophylaxis of thromboembolism associated with prosthetic heart valves. The most commonly reported adverse effects are headache, dizziness, diarrhoea, nausea (very common, $\geq 1/10$) and angina pectoris, vomiting, rash, myalgia (common, $\geq 1/100 < 1/10$).

Arm 4: Doxycycline

Doxycycline is licensed for use in the treatment of a variety of infections caused by susceptible strains of Gram-positive and Gram-negative bacteria and certain other micro-organisms. The most common adverse effects observed in patients receiving tetracyclines, including doxycycline, are hypersensitivity, headache, nausea/vomiting, photosensitivity reaction rash including maculopapular and erythematous rashes (common, $\geq 1/100 < 1/10$).

Management of risk is described in Appendix 1. However, this is the first use of these medications in this patient population, hence there is the *possibility* of additional unknown risks.

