6. PARTICIPANT ELIGIBILITY CRITERIA

6.1. Inclusion criteria

- ≥ 18 years.
- Able to provide informed consent.
- Capable of complying with all trial procedures and of completing the trial, in the opinion of the investigator.
- Bronchiectasis, confirmed by computed tomography (CT), showing bronchiectasis in 1 or more lobes.
- Normally produces sputum daily.
- Able to provide a sputum sample at the screening visit or between screening and randomisation^a.
- Active neutrophilic inflammation at screening/baseline indicated by a positive NEATstik (Neutrophil Elastase Airways Test) result^b.

^aRepeat sputum samples may be provided during the screening period, if the sample taken during the screening visit is deemed to be of insufficient quality or quantity by the laboratory.

^bA positive NEATstik test is equivalent to a NE concentration of 8 μ g/ml in sputum using the Proaxis active NE immunoassay. If NEATstik is not available for screening, a frozen sputum sample will be shipped to the central laboratory in Dundee where the immunoassay will be performed and used to confirm eligibility.

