6.3. Open treatment arm specific exclusion criteria

6.3.1. Arm 2: Disulfiram

- Currently on Disulfiram (patients should have a washout period of at least 30 days from last dose if they have previously received this medication)
- Hypersensitivity to Disulfiram
- Participant, or investigator objects to randomisation to Disulfiram
- Does not agree to cease consumption of alcohol during intervention and for 14 days following treatment discontinuation
- Chronic liver disease
- Alanine transaminase (ALT)>135 U/L at screening,
- Bilirubin >30 umol/L at screening.
- Uncompensated cardiac failure
- Coronary artery disease (diagnosis of stable or unstable angina, previous myocardial infarction)
- Previous history of stroke or transient ischaemic attack
- Uncontrolled hypertension
- Hereditary problems of galactose intolerance, total lactase deficiency or glucose-galactose malabsorption
- Recent psychiatric exacerbation
- Any significant acute or chronic psychiatric condition, including severe personality disorder, psychotic disorder or suicide risk.
- Hypothyroidism
- Porphyria

- Diabetes Mellitus
- Epilepsy

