6.3.3. Arm 4: Doxycycline

- Currently on Doxycycline (patients should have a washout period of at least 30 days from last dose if they have previously received this medication)
- Hypersensitivity to Doxycycline
- Participant, or investigator, objects to randomisation to Doxycycline
- Myasthenia Gravis
- Systemic Lupus Erythematosus
- Chronic Liver Disease
- Porphyria
- Alcohol dependence
- Suspected Syphilis

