7.3. Randomisation scheme

Participants will be randomised equally to any open arms they are eligible for. Participants will be allocated to an arm using a minimisation algorithm, with factors for centre, *Pseudomonas aeruginosa* infection recorded in the last 2 years and long-term use of macrolides.

Randomisation will initially open with a control arm and 3 treatment arms. When a treatment arm has recruited to its target, randomisation to that arm will be closed. When a new treatment arm is added, randomisation to that arm will be opened for all participants meeting the eligibility criteria for that arm.

Participants who have completed 56 days of follow-up (end of trial) may be rescreened and re-randomized if they are willing to participate in the trial again. Participants will receive a new copy of the current PIS, will be asked to complete a new Informed Consent Form, be given a new, unique participant identification number and eligibility will be rechecked prior to randomisation. All trial activities will be carried out as per protocol. Re-randomisation will be performed in the same way as for initial randomisations. Patients can be randomised a maximum of three times (i.e. initial randomisation and two re-randomisations).

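### One stated ground for disulfiram 400 mg is a cohort without alcohol dependence, but section 6.3.1 does not exclude dependence, although section 6.3.3 does for doxycycline

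*Protocol*

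**What the plan says.** Section 2 (Rationale, Arm 2: Disulfiram) first acknowledges the label: "While the SmPC states that the maximum Disulfiram dose is 200mg once daily". It notes that this limit belongs to treatment of alcohol dependence for up to six months. It then cites a BNF and clinical-practice maximum of 500 mg daily in the same condition, under supervision. It concludes that 400 mg for 28 days raises no major safety concern. That conclusion opens with "As the recruitment cohort are not individuals with alcohol dependency" and adds the exclusion of major cardiovascular, liver and psychiatric disease.

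Section 2.1 says of the disulfiram-ethanol reaction: "Symptoms may be severe and life-threatening".

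In section 6.3.1 the only criterion about alcohol excludes a person who "Does not agree to cease consumption of alcohol during intervention and for 14 days following treatment discontinuation". Section 6.3.3, for doxycycline, lists "Alcohol dependence". Under section 7.3, "Participants will be randomised equally to any open arms they are eligible for", and section 7.3.1 has eligibility assessed separately for each treatment arm.

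**The concern.** The rationale uses the absence of alcohol dependence as a safety argument for a dose above the cited label maximum. Where a dose argument depends on who is treated, the eligibility criteria should secure that population. Here they secure the other parts of the same sentence but not this one.

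What is at stake is the alcohol reaction. Appendix 1 says that its severity is related to disulfiram dose and ethanol intake, and that it has occurred at a blood alcohol of 10 mg/100 ml. A dependent participant plausibly has a higher risk of drinking during the 28 days of treatment or the 14 days after it, and would be taking twice the cited SmPC maximum.

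**Working it through.** The protocol gives no figure to reproduce on this point. The check is a comparison of sections with a little arithmetic.

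**1. Dose against the two cited maxima (section 2).**
- Against the SmPC: 400 / 200 = 2.0.
- Against the BNF and clinical practice: 400 / 500 = 0.8.
- Duration is 28 days, against up to six months in the SmPC context and a similar period for the BNF dose.

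**2. The safety sentence set against section 6.3.1.**
- Cardiovascular disease: carried over (uncompensated cardiac failure, coronary artery disease, previous stroke or transient ischaemic attack, uncontrolled hypertension).
- Liver disease: carried over (chronic liver disease, ALT above 135 U/L, bilirubin above 30 µmol/L).
- Psychiatric disease: carried over (recent psychiatric exacerbation, and "Any significant acute or chronic psychiatric condition, including severe personality disorder, psychotic disorder or suicide risk").
- Alcohol dependence: not carried over. Only the abstinence agreement concerns alcohol.

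**3. The criteria that apply to the disulfiram arm.** Section 6.1 has 7, section 6.2 has 13 and section 6.3.1 has 18: 7 + 13 + 18 = 38. None names alcohol dependence. Most of the 38 concern unrelated matters, so this count only confirms the absence. It does not measure importance. In section 6.3.3, 1 of 9 names it.

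**4. Whether the doxycycline exclusion carries over.** It does not, because eligibility is judged arm by arm (section 7.3.1). Take a dependent person who meets every other criterion, is eligible for dipyridamole, and is screened while all four arms are open. Doxycycline drops out, leaving usual care, disulfiram and dipyridamole. Equal allocation then gives a chance of disulfiram of about 1/3, against 1/4 for someone eligible for all arms. The figure is conditional on all those assumptions and shows only that the route is open.

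**5. Whether the BNF ground covers this person.** That dose is cited as given under supervision. Appendix 4 has drug dispensed once, at day 0, with accountability at day 28. Section 8.12 checks adherence by questions at visits and a tablet count at the last visit. No supervised dosing is described.

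**The case against.** The strongest reply is that the rationale does not depend on this premise. The BNF maximum of 500 mg exceeds the trial dose, applies to dependent patients themselves, and covers a much longer period. Clinical practice, trial safety data and the short duration are further grounds. This stands. A reader might infer that the case for 400 mg collapses if a dependent person enters the arm, and the protocol does not support that. What remains is the condition of supervision, which the trial does not reproduce.

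Second, the sentence can be read as describing people recruited for bronchiectasis, with only its second half claiming exclusions. That reading is fair, and on it there is no outright contradiction with section 6.3.1. But the description is still offered as a reason why the dose is safe, and having bronchiectasis does not rule out dependence.

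Third, the hazard is addressed directly. Participants are told of the reaction, must agree to abstain, and receive written advice on products containing alcohol (sections 2.1 and 8.11). The investigator must judge each one "Capable of complying with all trial procedures and of completing the trial, in the opinion of the investigator". The investigator or participant may object to disulfiram, the psychiatric exclusion is open-ended, the liver limits will remove some people, and the DMC reviews safety and compliance after the tenth participant in the arm reaches day 28 (section 10.4). These safeguards narrow the gap considerably. None of them requires a dependent person to be excluded.

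Fourth, the doxycycline exclusion may have its own reason, since section 8.9 lists alcohol as shortening doxycycline's half-life. So its presence in section 6.3.3 does not prove an oversight in section 6.3.1. It does show that the criterion can be listed and assessed.

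**Conclusion.** The point holds as a minor safety-consistency matter. One of several stated grounds for 400 mg is not secured by any criterion for the disulfiram arm. A dependent person who agrees to abstain and passes the liver, psychiatric and investigator-judgement criteria is excluded by name from doxycycline but not from disulfiram.

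The documents do not show that such people will be enrolled. They give no prevalence of dependence among candidates, so no head count is possible. The number is probably very small. Sample size, power, type I error and analysis are unaffected. The conclusion rests on the wording of sections 2, 6.1 to 6.3.3 and 7.3.1, and on the absence of any description of supervised dosing.

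**What to change.** Add alcohol dependence to the section 6.3.1 exclusions and to the arm-eligibility check recorded in the medical notes and eCRF under section 7.3.1. If the sponsor does intend to admit dependent people to this arm, drop the premise from section 2 and say why the 500 mg precedent applies without supervised dosing.

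The cost is one exclusion line and one eligibility item. The medical history in section 7.7 already covers chronic conditions related to the criteria, and sites already assess dependence for section 6.3.3, so no new procedure is needed. The downside is that at most a few participants become ineligible for disulfiram. They can still be randomised among the other arms for which they qualify.

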2.1. Assessment and Management of Risk

This trial is categorised as: Type B = Somewhat higher than the risk of standard medical care

The trial treatments are all repurposed drugs already approved for use in conditions other than bronchiectasis.

Arm 1: Usual care

Arm 2: Disulfiram

Disulfiram is an alcohol deterrent compound licensed for use as an adjuvant in the treatment of drinking problems. The most common adverse reaction (AR) reported during treatment is alcohol reaction. Disulfiram–ethanol reactions often develop within 15 minutes after exposure to ethanol; symptoms usually peak within 30 minutes to 1 hour, and then gradually subside over the next few hours. Symptoms may be severe and life-threatening. Participants will be informed of the reaction risk and must agree to abstain from alcohol during treatment and for up to 14 days after discontinuation.

Arm 3: Dipyridamole

Dipyridamole is licensed for use in secondary prevention of ischaemic stroke and transient ischaemic attacks and as an adjunct to oral anti-coagulation for prophylaxis of thromboembolism associated with prosthetic heart valves. The most commonly reported adverse effects are headache, dizziness, diarrhoea, nausea (very common, $\geq 1/10$) and angina pectoris, vomiting, rash, myalgia (common, $\geq 1/100 < 1/10$).

Arm 4: Doxycycline

Doxycycline is licensed for use in the treatment of a variety of infections caused by susceptible strains of Gram-positive and Gram-negative bacteria and certain other micro-organisms. The most common adverse effects observed in patients receiving tetracyclines, including doxycycline, are hypersensitivity, headache, nausea/vomiting, photosensitivity reaction rash including maculopapular and erythematous rashes (common, $\geq 1/100 < 1/10$).

Management of risk is described in Appendix 1. However, this is the first use of these medications in this patient population, hence there is the *possibility* of additional unknown risks.

3. OBJECTIVES AND OUTCOME MEASURES/ENDPOINTS

3.1. Table of endpoints/outcomes

Primary Objective		
Objective	Outcome Measures	Timepoint(s)
To evaluate the effect of a range of interventions compared to usual care on the activity of NE in sputum	Activity of sputum NE	Day 0 and 28
Secondary Objectives		
Objective	Outcome Measures	Timepoint(s)
To evaluate the effect of a range of interventions compared to usual care on the activity of NE in sputum	Activity of sputum NE	Days 0, 7, 14 and 56
To evaluate the effect of a range of interventions compared to usual care on time to onset of first bronchiectasis exacerbation	Time to first pulmonary exacerbation (EMBARC definition)	Days 0 to 28
To evaluate the effect of a range of interventions compared to usual care on quality of life	Quality of life-bronchiectasis (QOL-B) respiratory symptom scale, Bronchiectasis Impact Measure (BIM) questionnaire	Days 0, 7, 14, 28 and 56
To evaluate the effect of a range of interventions compared to usual care on clinical benefits	Bronchiectasis exacerbation and symptom tool (BEST) diary	Days 0 to 28
To evaluate the effect of a range of interventions compared to usual care on walking distance	Distance covered during 6-minute walk	Day 0, 28
To evaluate the safety of a range of interventions compared with usual care	Frequency of adverse events (AEs) and serious adverse events (SAEs)	Days 0 to 56
To evaluate the effect of a range of interventions on peripheral blood neutrophil function	Phagocytosis of bacteria Reactive oxygen species generation Degranulation Ex-vivo formation of neutrophil extracellular traps Mass cytometry (endpoints may vary depending on the experimental arm)	Day 0 to 28
Tertiary Objectives		
Objective	Outcome Measures	Timepoint(s)

To evaluate the effect of a range of interventions compared to usual care on bronchiectasis exacerbations	Frequency of pulmonary exacerbations (EMBARC definition)	Days 0 to 28; Days 0 to 56
To develop and validate additional biomarkers in sputum that are linked with clinical outcomes of bronchiectasis	Measure the concentration of MMPs and NETs in sputum, as well as other biomarkers e.g proteomics, bacterial load, microbiome	Days 0, 7, 14,28 and 56
To develop and validate additional biomarkers in blood that are linked with clinical outcomes of bronchiectasis	Measure serum biomarkers of inflammation and redox status	Days 0, 7, 14, 28 and 56
To investigate the effect of a range of interventions on peripheral blood neutrophils	Peripheral blood neutrophil proteomics performed on isolated cells	Days 0 and 28
To explore and characterise additional changes in inflammatory response in both sputum and blood across the range of interventions and usual care	Label free liquid chromatography/mass spectrometry sputum identification and relative quantification of proteins	Day 0 and 28
To explore changes in peripheral blood transcriptomics between interventions and usual care	Peripheral blood transcriptomics	Day 0 and 28
To explore changes in epithelial cell transcriptomics between interventions and usual care	Nasal brushing transcriptomics	Day 0 and 28
Sub-study Objectives		
Objective	Outcome Measures	Timepoint(s)
To evaluate the effect of a range of interventions compared to usual care on endothelial dysfunction	Change in skin perfusion with iontophoresis of acetylcholine and sodium nitroprusside using full-field laser perfusion imaging	Days 0, 28 and 56
To evaluate the effect of a range of interventions compared to usual care on the cardiovascular system	Change in arterial stiffness index	Days 0, 28 and 56
	Change in pulse wave velocity	

4. TRIAL DESIGN

Platform trial.

Parallel group design. Randomised, open-label, multifactorial, multicentre.

The trial will open to recruitment with a control arm and the first 3 treatment arms. Individual treatment arms will be closed for randomisation when the target for number of participants has been reached, or earlier if advised by the DMC and closed to follow up after Last Participant Last Visit (LPLV) for that arm. As new possibilities for treatments are identified additional treatment arms will be opened. Any new treatment arms will be submitted as an amendment to the current protocol. Randomisation to the control arm will continue for the duration of the trial.

4.1. Sub-study design

Participants enrolled within the Tayside site may be given the option of participation in the sub-study to examine endothelial and cardiovascular outcomes. The results from the sub-study assessments will be combined with results from separate trials, conducted in people with bronchiectasis, not connected with this protocol, for analysis.

5. TRIAL SETTING

AIR-NET will be conducted in a clinical trial network of 10 centres with capabilities to measure clinical and laboratory endpoints using the same optimised protocols. We will work with sites during the set-up phase of the study to standardise laboratory protocols for blood and sputum processing. The centres will be based in secondary care settings within the NHS in the UK.

5.1. Sub-study

Participants enrolled at the Tayside site.

6. PARTICIPANT ELIGIBILITY CRITERIA

6.1. Inclusion criteria

- ≥ 18 years.
- Able to provide informed consent.
- Capable of complying with all trial procedures and of completing the trial, in the opinion of the investigator.
- Bronchiectasis, confirmed by computed tomography (CT), showing bronchiectasis in 1 or more lobes.
- Normally produces sputum daily.
- Able to provide a sputum sample at the screening visit or between screening and randomisation^a.
- Active neutrophilic inflammation at screening/baseline indicated by a positive NEATstik (Neutrophil Elastase Airways Test) result^b.

^aRepeat sputum samples may be provided during the screening period, if the sample taken during the screening visit is deemed to be of insufficient quality or quantity by the laboratory.

^bA positive NEATstik test is equivalent to a NE concentration of 8 μ g/ml in sputum using the Proaxis active NE immunoassay. If NEATstik is not available for screening, a frozen sputum sample will be shipped to the central laboratory in Dundee where the immunoassay will be performed and used to confirm eligibility.

